Patient records will provide person-years of data for each study cohort (Exposed and Unexposed). The incidence rates will be assessed for both the exposure and non-exposure cohorts. The incidence rates will also be assessed for both the follow-up time periods prior to and after the initial date of receiving romiplostim in the Exposed Cohort.

When sample size permits, Kaplan-Meier survival curves will be constructed for patients with events of interest for the Exposed Cohort and Unexposed Cohort.

Due to the intrinsic limitations of this type of observational study, the effects of confounding by indication may bias the results when the incidence rates of study outcomes are compared between the Exposed Cohort and Unexposed Cohort. The effects associated with confounding by indication will be considered in all analyses in order to reduce the possible impact of these effects in the comparison.

In order to reduce the effects of confounding by indication, a propensity score will be developed for each adult chronic ITP patient. A stratified analysis (by propensity score strata, disease severity, and platelet count) and multiple regression analyses will be carried out. As needed, the age-, sex-, and propensity score-matched approach may be also applied to the adult chronic ITP study population. (Inherent limitations related to propensity score are addressed in [Section 8](#)).

Cox regression models using romiplostim exposure as a time-varying covariate may be used to compare the event rates among ITP patients and the reference cohort, with an estimation of the hazard ratio and associated 2-sided 95% confidence interval. Other treatment exposures, health status, and disease condition may also be considered for inclusion in the model as time-varying covariates. The analysis will adjust for potential confounders and propensity score. Multiple event models such as Andersen-Gill models may be used to evaluate recurrent events if applicable. However, this analysis is only intended to serve exploratory and hypothesis generation purposes.

Means and 95% confidence intervals of laboratory numerical outcomes (eg, platelet counts) will be obtained and compared between the associated cohorts, and among different predefined time periods related to romiplostim treatment ([Section 7.1](#)).

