- Total number of subjects and total person-year observation time in each cohort for the current reporting period, and cumulative for all reporting periods
- Current incidence rates of study outcomes based upon data in the current reporting period, and upon cumulative data for all reporting period
- Average platelet counts in predefined romiplostim treatment periods
- Detailed descriptions of each case of BM fibrosis associated with clinical signs in the current reporting period
- Detailed description of hematological malignancy cases (eg, AML and MDS)

[figure not shown]
A final report to the regulatory agency will be completed within 9 months following the availability of all national data. The final report will be comprehensive for all primary and secondary objectives, and for related outcomes listed in [Section 12](#).

Expected Contribution of Study Results to Current Knowledge

- Determine acute and long-term safety in real life clinical practice
- Describe the impact of romiplostim therapy on platelet count during treatment, and changes after treatment cessation
- Describe the impact of romiplostim therapy on BM fibrosis
- Describe romiplostim off-label utilization pattern

Sponsor/Licensee: Amgen Inc.

Study Design and Patient Registry Schema

Study Glossary and Definition

Abbreviation/Acronym	Definition
AGS	Amgen Global Safety
AML	Acute myelogenous leukemia
BM	Bone marrow
Chronic ITP cITP	Patients who have been diagnosed with ITP for more than 6 months, and who continually receive ITP treatments (eg, ITP related medication) and/or have had a splenectomy procedure
CIMF	Chronic idiopathic myelofibrosis (primary myelofibrosis)
Confounders	Extraneous factors that account for a difference in disease frequency between the exposure groups; associated factors serving as surrogates for these factors are also commonly called confounders
ICD-10	International Classification of Diseases – 10 th Revision
Index date	Date the patient received initial romiplostim therapy in the study period, and the start date of follow-up for each study subject in the Unexposed Cohort
ITP	Idiopathic (immune) thrombocytopenic purpura
Length of disease	Time period from initial diagnosis of the disease to date of study event
MDS	Myelodysplastic syndromes
NCPRR	Nordic Country Patient Registry for Romiplostim
NHRS	National Health Registry System

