Case ascertainment and confirmation: Diagnosis based on ICD-10 codes may not be able to correctly determine outcomes. The sensitivity and specificity of diagnosis based on ICD-10 codes for different diseases and conditions and for different cohorts may vary, and may induce a bias. To address this issue, the study will review electronic medical charts to confirm a diagnosis beyond ICD-10, as well as laboratory data and BM biopsy as needed.

Selection bias due to missing values: The study is based on the NHRS databases. Information for some key covariates (eg, laboratory data) may be missing for some patients. It is possible to introduce a selection bias if patients with missing values are excluded from a particular analysis. The missing value issue may also occur in development of propensity score. Patients with missing values will be excluded from the propensity development model. To address this issue, statistical methods will be employed: 1) to evaluate the mechanism of the “missingness” and 2) to impute values for missing variables based on patterns of “missingness”, if necessary.

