There are many factors that may affect the adult chronic ITP disease condition (eg, age, sex, length of disease, severity, platelet counts, splenectomy, co-morbidities, and concurrent medications). To reduce potential effects from confounding by indication of romiplostim therapy, a propensity score will be developed to create a pseudo-randomization in balancing important factors that might affect the outcomes between the romiplostim Exposed Cohort and Unexposed Cohort for chronic ITP patients. The propensity score is defined as the conditional probability of being treated given a set of important and relevant covariates. The logistic regression method will be used to develop the propensity score for the severity of the ITP condition. The variables to be considered may include, but are not limited to, age, sex, BMI/BSI, country, year of ITP diagnosis, length of disease, average platelet counts, lowest platelet counts, splenectomy, major comorbidities, and prior ITP medications (type and frequency), and frequency and severity of bleeding events. While the propensity score is being developed, other methods, such as stratification by country or by a span of years associated with changing practice patterns will be investigated. The aforementioned variables to be included in the propensity score development model will be updated and modified based upon the findings from an Amgen-sponsored historical study to be based upon the Danish Health Registry System Database for chronic ITP patients (Study 20070796) and expert opinions. The dependent variable for the model is romiplostim therapy (yes or no). The propensity model will be refined with every annual analysis based on newly available data. The propensity score will be reassigned to each patient for each annual analysis and the final analysis; therefore, the propensity-score for each subject in the cohorts reported in each annual and the final analysis may be different. However, variables involved in the propensity score development model will be the same throughout unless some new variable emerged during the 11-year study period. The data used to develop a propensity score will be from 6 months prior to the Index Date of receiving romiplostim therapy, and data from 6 months prior to the Index Date that is randomly selected from romiplostim-unexposed chronic ITP patients. To ensure the sensitivity and specificity of the propensity score, sensitivity analyses will be conducted for each established propensity model. The sensitivity and specificity test will be conducted using medical records for selected clinical characteristics, features, severity measures, and potential confounders.

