
The distribution of propensity scores for the Exposed Cohort and Unexposed Cohort will be graphically presented in a figure. Patients with very low or very high propensity scores whose scores are non-overlapping with patients in comparison cohorts will be excluded from (or trimmed from) the analysis. The “trimming” method will remove outliers from the analysis to reduce selection bias and the impact of patients with extreme conditions. This may impact the statistical power to evaluate any differences between the exposed and unexposed groups. A reduced sample size would reduce the probability of detecting a difference in a range of relative risks from 2 to 4 where the background incidence ranges from 0.5% to 5% (refer to [Appendix 1](#) for exact power). Based upon the distribution of propensity scores, 5 strata will be developed and used in the analysis. Propensity scores will also be used in multiple regression analysis as a covariate. Important variables including age, sex, ITP diagnostic year and disease duration that contribute to the propensity score can also be independently included in multiple regression analysis as additional covariates, which constitute a “Doubly Robust” model.

The propensity score, along with age, sex and diagnosis year will be used as needed to match the Exposed Cohort and Unexposed Cohort among adult chronic ITP patients.

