12.7 Stratified Analysis

Stratified analyses will be used as needed. The following are some variables to be considered as stratification factors:

- Sex and age (< 18, 18 to 30, 31 to 50, 51 to 70, and 71+)
- BMI and/or BSI
- Propensity scores (5 strata)
- Initial platelet level (< 10×10^9 , 10 to 30×10^9 , ≥ 30 to 50×10^9)
- Length of chronic ITP since diagnosis (< 1 year, 1 to 3 years, 4+ years)
- Year of initial ITP diagnosis (1996 to 2000, 2001 to 2005, 2006 to 2010, 2011 to 2015, and 2016 to 2018)
- Splenectomy (yes or no)
- Receiving immunosuppressive therapy
- Concomitant bleeding disorder/history of significant bleeding
- Any significant span of years (based on changing practice patterns)
- Country (if practice patterns differ among studied countries)

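### The glossary runs length of disease to the study event, although it serves as a baseline propensity and regression covariate; the platelet strata in Section 12.7 are also incomplete and overlap.

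*Protocol*

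**What the plan says.** The Study Glossary defines length of disease as "Time period from initial diagnosis of the disease to date of study event". No other section redefines the term.

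It is used in these places:

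- Section 6.3 names it among the disease conditions that are key variables in the analysis.
- Section 12.3 lists it for the logistic propensity model: "year of ITP diagnosis, length of disease, average platelet counts, lowest platelet counts, splenectomy".
- Section 12.3 also allows variables to enter the regression beside the score: "Important variables including age, sex, ITP diagnostic year and disease duration that contribute to the propensity score".

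On timing, Section 12.3 states: "The data used to develop a propensity score will be from 6 months prior to the Index Date of receiving romiplostim therapy". Section 7.1 likewise assigns propensity scores in the baseline period before treatment.

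On stratification, the Synopsis (Statistical Considerations) states: "A stratified analysis (by propensity score strata, disease severity, and platelet count) and multiple regression analyses will be carried out". Section 12.7 lists three bands of initial platelet level (x 10^9/L): below 10, 10 to 30, and from 30 up to 50. Section 3.4.2 excludes patients who have no count below 150 around the first ITP code. Section 6.3 prints a diagnosis-year band of 2010 to 2015, following one that ends in 2010. The Synopsis, Section 3.1 and Section 12.7 all print 2011 to 2015.

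**The concern.** Section 8 expects patients with longer and more severe disease to be the ones given romiplostim. Disease duration is therefore one of the main confounders that the adjusted comparisons must handle, and it has to be measured on the same footing for every patient, at a point before outcomes can occur. The glossary instead ties its end to the outcome. An analyst who follows that definition would adjust for a quantity that contains the event time, and would have to invent a value for everyone without an event.

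The comparisons are labelled exploratory, but they are meant to pick up safety signals, and annual results go to the regulator. A distorted adjustment could create a signal or hide one.

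The platelet bands raise a smaller problem of the same kind: eligible patients can have an initial count that fits no listed band.

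**Working it through.** The protocol states no figure for this point, so there is none to reproduce. The check sets the definitions side by side and then illustrates the consequence.

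**1. What the definition contains.** Let d0 be the time from initial diagnosis to Index Date, and y the time from Index Date to the event. The glossary value is

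D = d0 + y.

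- Without an event, y has no end date and D is undefined.
- With several of the outcomes in Section 6.2, there are several values of y and so several values of D. Section 12.3 gives each patient one propensity score per analysis.
- With an event, D includes y, which is the response in a time-to-event model.

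**2. Conflict with the propensity window.** Section 12.3 draws propensity data from the 6 months before the Index Date. Time at risk starts only after first exposure or at the Index Date (Section 7.3). A counted event therefore falls after the window has closed, and D cannot be built from data inside it. The two statements cannot both hold.

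**3. Why a fixed D biases a Cox model.** At an event time t, the patient with the event has D = d0 + t. Everyone else in the risk set has D = d0 + y with y at least t. The case tends to have the smallest D, so longer duration looks protective whatever the truth. If d0 also differs between cohorts, the exposure coefficient takes up part of that error.

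**4. Illustration by simulation.** From the protocol: 623 exposed and 1860 unexposed patients (Sections 3.5 and 11). Assumed, not from the protocol:

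- event rates of 0.5% and 5% per year (Section 11 gives 0.5% to 5% as background incidence without stating a time unit);
- exponential prior duration with mean 4 years (exposed) and 3 years (unexposed);
- follow-up uniform from 1 to 11 years;
- no true effect of prior duration;
- D run to the censoring date for event-free patients, since the glossary supplies no date.

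There were 60 runs per setting.

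| True exposure HR | Rate per year | Exposure HR, duration to Index Date | Exposure HR, duration to event or censoring | Duration HR per year, to Index Date | Duration HR per year, to event or censoring |
|---|---|---|---|---|---|
| 1.0 | 0.5% | 0.97 | 1.16 | 0.997 | 0.642 |
| 1.0 | 5% | 0.99 | 1.18 | 0.999 | 0.670 |
| 2.0 | 0.5% | 2.03 | 2.33 | 0.998 | 0.660 |
| 2.0 | 5% | 2.01 | 2.10 | 0.999 | 0.697 |

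The exposure HR rises by a factor of 2.10/2.01 = 1.04 to 1.16/0.97 = 1.20. Duration looks strongly protective although it has no effect. Measured to the Index Date, both coefficients come back close to the truth.

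**5. Platelet bands in Section 12.7 (x 10^9/L).** Test values of 5, 10 and 50 each fall in one band. A value of 30 falls in two. Values of 51, 75, 100 and 149 fall in none. Below the limit of 150, 150 - 50 = 100 units of the scale have no band; this is a span of values, not a share of patients. Section 3.4.2 asks only for some count below 150 within 6 months either side of the first code, so an initial count could itself be 150 or more.

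**6. Diagnosis year.** As printed in Section 6.3, 2010 belongs to two bands. The other three places agree on 2011 to 2015, so this is a misprint.

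**The case against.** The strongest reply is that the operative sections already place the propensity score at baseline: Section 7.1 assigns it before treatment, Section 8 compares patients as they start romiplostim, and Section 12.3 fixes the 6-month window. This stands. A reader might infer that the propensity score becomes a function of the outcome, but the documents support only a contradiction between the glossary and those sections.

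For the regression covariate, the Synopsis and Section 12.4 allow disease condition as a time-varying covariate, and time since diagnosis updated within each risk set would be valid. This stands in part. The glossary does not say a fixed value is meant, but it does not say a time-updated one is meant either, and here no data window protects the covariate.

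Three further inferences are tempting and not supported:

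- That event-free patients would drop out because of Section 8: "Patients with missing values will be excluded from the propensity development model". That sentence concerns information missing from the registries, and the same paragraph provides for imputation. Nor can the share of patients without any event be derived, because Section 6.2 covers many outcomes.
- That patients with counts above 50 would be lost from the analysis. Section 12.7 offers its strata for use as needed, the Synopsis commits to stratifying by platelet count but not to these cut-points, and nothing says what happens to unclassified patients. Their number is not given.
- That other items in Section 12.7 are broken. An age band below 18 can serve paediatric off-label users, whom the registry includes. The item "Length of chronic ITP since diagnosis (< 1 year, 1 to 3 years, 4+ years" has no gap if completed years are meant.

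Finally, the primary objective is an incidence rate in exposed patients, and all comparisons are declared exploratory. This stands and limits the severity.

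**Conclusion.** The point holds, at moderate severity. As written, the glossary definition cannot serve as a covariate: it is undefined without an event, not unique with several events, and it includes follow-up time. In the propensity model it contradicts Section 12.3. As a fixed regression covariate it would bias the exposure effect. The simulated inflation of 4% to 20% in the hazard ratio illustrates the mechanism only; it rests on the assumed durations, rates and follow-up, and other assumptions could change its size or direction.

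The platelet bands are incomplete above 50 and overlap at 30, against a Synopsis commitment to stratify by platelet count. This and the misprinted year band are secondary. The primary incidence estimate is unaffected.

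**What to change.** 1. **Glossary.** Define length of disease as the time from initial ITP diagnosis to Index Date, and use that value in Sections 6.3 and 12.3. Where time since diagnosis is wanted during follow-up, allow it only as a time-updated covariate or as the time scale of the Cox model.
2. **Section 12.7.** Make the initial platelet bands (x 10^9/L) exhaustive and non-overlapping: below 10, 10 to below 30, 30 to below 50, and 50 or more. The top band should be open, because eligibility does not cap the initial count at 150.
3. **Section 6.3.** Change 2010 to 2015 to 2011 to 2015.

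The cost is three text edits and no new data, since Section 4.1 already defines Index Dates for both cohorts. One consequence needs settling in the same edit. Section 4.1 sets the Index Date of an unexposed patient diagnosed on or after 01 April 2009 to the date of diagnosis. If that means the initial ITP diagnosis, length of disease is zero for all such patients by construction. Section 12.3 can be read as using a randomly selected Index Date instead. The protocol should say which Index Date the covariate uses.

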1. OBJECTIVES

The purpose of the Nordic Country Patient Registry for Romiplostim (NCPRR) is to assess the safety of romiplostim in post-marketing clinical practice settings. Since the study period will be of 11 years duration, the study will provide an infrastructure to assess the long-term risk profile of the product. The study may also be used to assess any newly identified safety signals during post-marketing periods. However, the primary purpose of the NCPRR is to fulfill romiplostim post-approval pharmacovigilance (PV) requirements of the European regulatory agency.

1.1 Primary Objective

- To estimate the incidence rate of increased bone marrow (BM) reticulin and/or BM fibrosis with associated clinical signs³, confirmed by BM biopsy findings of adults with chronic ITP receiving romiplostim

1.2 Secondary Objectives

Potential clinical risks:

- To describe the phenomenon of worsened thrombocytopenia (platelet count significantly reduced to, or below, baseline platelet count levels) after romiplostim cessation among adult chronic ITP patients
- To study the incidence rate of thrombocytosis (platelet count $> 450 \times 10^9/L$) among romiplostim-treated adult chronic ITP patients with/without adverse events
- To describe the incidence rate of thrombotic/thromboembolic events and the distribution of specific diagnoses of these thrombotic/thromboembolic events for a romiplostim-exposed cohort and an unexposed cohort
- To assess the incidence rate of hematological malignancies and pre-malignant states (focused on acute myelogenous leukemia [AML] and myelodysplastic syndromes [MDS]) for a romiplostim-exposed cohort and an unexposed cohort
- To describe clinically significant bleeding and/or receipt of rescue medication (any new ITP medication prescribed to a chronic ITP patient during romiplostim therapy) in predefined romiplostim therapy periods ([Section 7.1](#))
- To describe the incidence rate of concurrent leukocytosis and anemia (measured by laboratory test results taken within 4 weeks of each other)

³ Clinical signs: any of the following: splenomegaly, hepatomegaly, leukocytosis, and cytopenia

- To describe patient safety profiles, including the incidence rate of renal failure among adult chronic ITP patients with renal impairment medical condition when romiplostim therapy is initiated
- To measure the impact of the EU dosing rule in the cohort of romiplostim exposed patients

Potential BM abnormal findings:

- To describe the prevalence of reticulin and collagen fiber content in the first BM biopsy of adult chronic ITP patients prior to romiplostim exposure, by splenectomy status
- To assess the incidence of collagen fibrosis with associated clinical signs confirmed by findings in BM biopsies of adults with chronic ITP either receiving or not receiving romiplostim
- To study the incidence of chronic idiopathic myelofibrosis (CIMF, primary myelofibrosis) according to the WHO diagnostic criteria in adults with chronic ITP either receiving or not receiving romiplostim
- To assess overall and specific incidence of BM fibrosis, including reticulin and collagen fiber content formation, and CIMF among adult chronic ITP patients with BM data prior to and following romiplostim therapy, regardless of clinical signs and symptoms in adults with chronic ITP either receiving or not receiving romiplostim

Romiplostim Off-label Use

- To describe the romiplostim utilization pattern in patients without adult chronic ITP

